## Study center(s) and number of subjects planned

The study will include a total of 44 subjects equally distributed at two centers:

Center 1: [name], University of Maryland, USA Center 2: [name], University of Iowa, USA

### Study timetable

Estimated date of first subject April 2016 enrolled

Estimated date of last subject

April 2017

completed implant placement

80

Estimated date of last subject completed follow-up period

September 2018

## **Objectives**

The primary objective of this study is to investigate linear and volumetric osseous changes at 4 months following ridge preservation by calculating horizontal and vertical bone changes via cone beam computed tomography (CBCT).

The secondary objectives of the study are to evaluate:

- New bone replacement/remaining graft residuals at re-entry (histomorphometric assessment).
- Change in mesial and distal marginal bone loss on periapical radiographs from baseline to re-entry.
- Change in mesial and distal marginal bone loss on periapical radiographs from crown delivery to 6 months and to 12 months after the crown delivery (follow-up observation).

#### Study design

The study is designed as a randomized controlled clinical trial. Patients will be assigned for ridge preservation of a single extraction socket site to treatment group A (GUIDOR® easy-graft CLASSIC) or group B (Freeze-dried bone allograft (FDBA) with collagen plug).

VERSION 1.1 2(33)

The study will involve a ridge preservation procedure and the follow-up observation period in 12 months after delivery of implant-supported prosthesis. The study randomization key will be opened after completion of re-entry visit of all patients for analysis of the primary endpoint. However, examiners and central reading centers will have to be masked until the end of study.

### Target subject population

Patients in need of ridge preservation prior to dental implant therapy in a single extraction socket in premolars and molars except for third molar will be included.

## **Investigational product**

GUIDOR® easy-graft CLASSIC is a bone graft substitute consisting of pure beta-triphosphate calcium ( $\beta$ -TCP) coated by poly (lactic-co-glycolic acid) (PLGA) and BioLinkerTM. BioLinkerTM is comprised of N-methyl-2-pyrrolidone (NMP). The particle size is 500– 1000  $\mu$ m and is sterilized by gamma sterilization process. The mixture of grafting material and BioLinker get hardening into a stable, porous immediately after the mixture contacts blood or body fluid in a defect.

## Comparator, dosage, and mode of administration

Mineralized cortical freeze-dried particulate bone allograft (FDBA) has a particle size of 250-1000 μm (Lifenet). It is sterilized via Allowash XG® technology.

Collagen plug (Zimmer Dental Inc.), is made from a bovine type I collagen. The resorption period is 10-14 days.

#### **Duration of treatment**

The study will be a five month follow up to re-entry for implant placement. The treatment period includes ridge preservation followed by implant placement 5 months later. Follow-up visits following the ridge preservation will occur at one week, two weeks, 4 weeks, 2 months, 4 months (CBCT) and 5 months (re-entry and implant placement).

Follow-up observation after the implant placement will occur at the crown delivery, 6 months and 12 months.

#### **Outcome variables**

#### **Efficacy**

#### **Primary outcome variable:**

Linear and volumetric horizontal and vertical bone changes at 4 months

#### Secondary outcome variables:

- Qualitative histology: new bone and residual graft particles

VERSION 1.1 3(33)

 Mesial and distal marginal bone loss on periapical radiographs at reentry and follow-up period after crown delivery.

## **Safety**

- Complications
- Adverse events

#### Statistical methods

The primary outcome variables of dimensional horizontal and vertical bone changes will be analyzed by Wilcoxon rank sum test.

The secondary outcome variable assessing new bone formation and residual graft particles, and mesial/distal bone loss will be analyzed by Wilcoxon rank sum test.

VERSION 1.1 4(33)

## 1 INTRODUCTION

# 1.1 Background

A horizontal loss of some 15% of the original width of the alveolar ridge already occurs in the first 6–8 weeks after tooth loss. A broad systematic analysis of the relevant literature showed that vertical loss in the first 6 months equals about 1.2 mm which is about 11–22% of the original height (1). With physiological loss of hard and soft tissue following tooth extraction, the conditions deteriorate for proper axial alignment of the implant and aesthetically pleasing prosthetic treatment (2, 3).

To minimize alveolar atrophy in the course of wound healing, method has been described that is summarized under the terms "ridge preservation". This typically involves filling the extraction socket with bone or bone graft substitute and/or covering it with a membrane. When a tooth is extracted atraumatically without raising a flap the bone graft substitute can be plugged by a collagen plug. The primary objective of ridge preservation is preserving the alveolar ridge volume. A systematic literature analysis shows that ridge preservation procedures are effective. With ridge preservation procedures, alveolar atrophy in the first 6 months after tooth extraction is significantly lower than atrophy in non-treated control groups (4).

Evidence-based reviews have shown positive outcomes using a broad range of grafting materials, including autogenous bone, allografts, and xenografts in ridge preservation procedures (5, 6). Synthetic bone grafting materials are made from mineral raw materials. The most-used materials are  $\beta$  -tricalcium phosphate ( $\beta$ -TCP), hydroxyapatitie (HA) and biphasic calcium phosphate. Human bone consists of approximately 60-70% of a modified hydroxyapatitie (HA) and 30-40% of organic constituents and water, this material can give bone its strength (7, 8).

Easy-graft® CLASSIC, is commercially available alloplastic bone graft granules consists of pure β-TCP, which has been commonly used for the indication of ridge preservation (9). It has unique handling capacity based on an extremely thin coating of the graft granules with poly(lactic-co-glycolic acid) (PLGA). In medicine, PLGA is used to manufacture dental membranes, suture materials and resorbable screws. Before application, the granules are mixed with BioLinker™ which consists of water and N-Methyl-2-pyrrolidone (NMP). It is non-volatile solvent which has been in used in various medical products for more than 10 years. Easy-graft remains moldable until it comes in contact with blood or tissue fluids. When the material is soaked in blood in bone defects it hardens in a few minutes to form stable porous scaffold for bone regeneration. This characteristic of graft material gives better handling for the clinician.

The pilot case study aiming to evaluate the performance of easy-graft CLASSIC in extraction socket ridge preservation has been conducted by University of Maryland School of Dentistry (IRB# HP00063203). The interim observation of the study indicates that the effectiveness of easy-graft CLASSIC is not inferior to those of other leading bone graft substitutes even when easy-graft is used without a membrane or a plug

VERSION 1.1 5(33)

covering the defect site. It is beneficial to both dentists and patients to avoid additional treatment time and a cost of membrane or a plug.

The purpose of study is to evaluate two different treatment approaches using easy-graft CLASSIC for comparative effectiveness to freeze-dried bone allograft (FDBA) with collagen plug (Collagen Plug, Zimmer Dental Inc.) in ridge preservation when the study tooth is extracted atraumatically. Furthermore, implant stability will be observed in the follow-up period.

# 2 STUDY OBJECTIVES

# 2.1 Primary objective

The primary objective is to assess horizontal and vertical linear and volumetric osseous changes after single tooth extraction and the application of two different ridge preservation techniques, via DICOM data analysis. The changes from baseline to four months will be compared. Radiographic measurements will be obtained from DICOM data files acquired by CBCT imaging.

**Hypothesis**: The treatment group with easy-graft CLASSIC is superior or at least not inferior to the control treatment group (FDBA with collagen plug).

# 2.2 Secondary objectives

Secondary objectives of the study are to evaluate and compare:

- New bone replacement/remaining graft residuals at re-entry (histomorphometric assessment).
- Change of mesial and distal marginal bone loss on periapical radiographs from baseline to re-entry.
- Change of mesial and distal marginal bone loss on periapical radiographs from crown delivery to 6 months and to 12 months after the crown delivery (follow-up observation).

VERSION 1.1 6(33)

# 3 STUDY PLAN AND PROCEDURES

# 3.1 Overall study design and flow chart

The study is designed as a randomized control prospective study with two study centers.

The study population will consist of individuals requiring ridge preservation prior to dental implant therapy in a single tooth extraction socket in premolars and molars except for third molars.

A total of 44 subjects will be randomized to obtain at least 40 evaluable subjects in anticipation of a 10% dropout rate. 44 evaluable subjects will be enrolled at two centers. Each subject will be randomized into one of two groups: group A (GUIDOR® easy-graft CLASSIC) and group B (FDBA and collagen plug). Each center will enroll 22 evaluable subjects, 11 per group ideally.

The ridge preservation study will be a 5-month follow-up with 9 main clinic visits to reentry/implant placement. Three additional clinic visits for the observation period will be scheduled after crown delivery to the study site.

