### Procedures for handling incorrect enrolled subjects

Subjects not meeting the inclusion/exclusion criteria for a study should, under no circumstances, be enrolled into the study - there can be no exceptions to this rule. When subjects not meeting the study criteria are enrolled in error, or if subjects subsequently fail to meet the criteria for the study after enrollment, they will be excluded from the study and from the analyses.

If subjects are excluded intraoperatively (e.g. dehiscence), the subjects will receive a standard grafting treatment at no cost. However, an implant placement at the site will be at the patient's cost.

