# 3.4 Method of assigning subjects to treatment groups

Screening numbers will be assigned at day of screening (Visit 1). Subjects at center 1 will receive numbers starting at S101 and subjects at center 2 will receive numbers starting at S201. Subject numbers (subject ID) will be consecutively allocated in series at day of inclusion (Visit 2). Subjects at center 1 will receive numbers starting

VERSION 1.1 19(33)

at 101 and subjects at center 2 will receive numbers starting at 201. Enrollment will continue until 22 subjects at each center have been allocated a subject ID. If a subject discontinues, the subject number will not be reused.

Subjects will be randomized strictly sequentially at enrollment (Visit 2). The randomization schedule will be generated using a validated system under the responsibility of the data management team. The randomization procedure will be concealed. Randomization will be stratified by center and smoking habit, i.e. each center will have 11 subjects in each group A and B, respectively with an equal number of subjects with current tobacco consumption per group. The allocation will be revealed to the clinician only following tooth extraction for ridge preservation.

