# 6.1.3 Handling of dropouts and missing data

Patients dropping out from the trial prior to study end will not be replaced. Data totally missing will not be estimated.

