# 6.3 Determination of sample size

A sample size of 22 participants per treatment group was selected following power calculations and allowing for 10% patient dropout. A sample size of 20 patients was calculated for the primary outcome variable (horizontal bone changes) with the assumption that the detectable difference would amount to 0.7 mm with a standard deviation of 0.8. The type I error probability was set at 0.05 and the statistical power was set at 80%.

VERSION 1.1 28(33)

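### Section 3.1 gives two incompatible evaluable targets (at least 40, and 44), and 20 per arm does not reach the stated 80% power on the plan's own inputs

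*Combined protocol and SAP*

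**What the plan says.** Section 3.1 (Overall study design and flow chart) sets the sample size in three consecutive sentences:

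- On the number randomized and its purpose: "A total of 44 subjects will be randomized to obtain at least 40 evaluable subjects in anticipation of a 10% dropout rate"
- On the number to be enrolled, in the sentence that follows: "44 evaluable subjects will be enrolled at two centers"
- After a sentence on the two groups: "Each center will enroll 22 evaluable subjects, 11 per group ideally"

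Section 6.3 (Determination of sample size) states: "A sample size of 22 participants per treatment group was selected following power calculations and allowing for 10% patient dropout". It gives 20 as the number before that allowance, for a difference of 0.7 mm, SD 0.8, type I error 0.05 and 80% power. It states no inflation formula.

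Three other sections fix how many subjects can contribute data:

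- Section 3.4: "Enrollment will continue until 22 subjects at each center have been allocated a subject ID". The number of a subject who discontinues is not reused.
- Section 6.1.3: "Patients dropping out from the trial prior to study end will not be replaced", and "Data totally missing will not be estimated".
- Section 3.2.5, on subjects enrolled in error or later found not to meet the criteria: "they will be excluded from the study and from the analyses".

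Section 6.1 makes all p-values two-sided, and section 6.2.1 tests the primary hypothesis with the Wilcoxon rank sum test.

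**The concern.** The first sentence of section 3.1 treats 44 as the number randomized, from which losses are subtracted. The second and third treat 44 (22 per center) as the number left for analysis. No mechanism closes the gap: enrolment is capped, losses are not replaced, and missing data are not imputed. A site reading section 3.1 could think it should go on until 22 subjects are evaluable; section 3.4 tells it to stop at 22 IDs.

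The evaluable number also carries the power claim. If the intended number is about 20 per arm, the stated 80% should hold there, and the dropout allowance should deliver that number. Both can be checked from the plan's figures. There is little reserve, because randomization takes place at Visit 2 while dehiscence, fenestration or buccal fracture found at surgery removes a subject afterwards. The documents do not say whether the 10% covers these exclusions.

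**Working it through.** **Inputs.** Randomized 44, i.e. 22 per arm and 22 per center (sections 3.1, 3.4, 6.3). Loss 10% (sections 3.1, 6.3). Difference 0.7 mm, SD 0.8, alpha 0.05, power 80% (section 6.3). Two-sided (section 6.1). The 20 in section 6.3 is read as per arm, because 22 per arm is derived from it and section 3.1 gives a total of 40.

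**1. The plan's base figure.** Normal formula, n per arm = 2 x [SD x (z for 0.975 + z for 0.80) / difference]^2 = 2 x [0.8 x (1.960 + 0.842) / 0.7]^2 = 20.5, which rounds up to 21. The t-test solution is 21.5, so 22. The stated 20 is close but slightly low.

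**2. Power at 20 per arm.** Standardized difference = 0.7 / 0.8 = 0.875.

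- Normal formula: Phi(0.875 x sqrt(20/2) - 1.960) = Phi(2.767 - 1.960) = Phi(0.807) = 79.0%.
- Two-sample t-test: 76.9%.
- Wilcoxon rank sum test with normal data: multiplying n by the asymptotic relative efficiency 3/pi and using the t-test gives 74.9%. Simulation also gives about 75%.

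**3. Evaluable number at 10% loss.** 44 x 0.9 = 39.6 in total and 22 x 0.9 = 19.8 per arm. Four losses (4/44 = 9.1%) leave exactly 40; five (5/44 = 11.4%) leave 39. Dividing the target by 0.9 gives 40/0.9 = 44.4, so 45 in total. Per arm it gives 20/0.9 = 22.2, so 23, or 46 with equal arms. That is 1 to 2 subjects above the stated 44.

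**4. Cost of that shortfall.**

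| Method | 20 per arm | 19.8 per arm |
|---|---|---|
| Normal formula | 79.0% | 78.6% |
| t-test | 76.9% | 76.5% |
| Wilcoxon (3/pi) | 74.9% | 74.5% |

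The difference is about 0.4 points in each row.

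**5. The two targets side by side.** Under the cap and the no-replacement rule, evaluable = 44 minus those lost before the primary measurement. Setting this to 44 requires zero such losses. Setting it to at least 40 allows four. The first sentence of section 3.1 plans for about four, so the 44 evaluable in the next sentence contradicts it.

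**The case against.** The strongest reply is that conduct is not in doubt. The planned total, the ID cap in section 3.4 and the group size in section 6.3 all agree on 44, so nobody would enrol a different number, and evaluable in the second sentence may simply mean eligible at enrolment. The agreement on 44 enrolled is real and is why enrolment need not change. The softer reading of the word is weak, because one sentence earlier it plainly means remaining after dropout, and the plan defines it nowhere.

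Three stronger readings may tempt a reader, and the documents do not support them:

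- **44 is a wrong sample size.** The gap is 0.4 of a subject and about 0.4 points of power. A size set on expected loss meets its target only part of the time in any case.
- **The allowance was made by multiplying 20 by 1.1.** That reproduces 22, but section 6.3 gives no formula, so the cause is a guess.
- **Any dropout at all rules out 44 evaluable.** Section 6.1.3 speaks of leaving before study end, and follow-up runs to 12 months after prosthesis delivery. The primary outcome is measured at Visit 8 (4 months). A subject who leaves after that scan still has primary data. Only losses before it count.

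It is also fair to say that the shortfall from 80% exists at 20 per arm before any dropout, so it belongs to the base calculation and not to the dropout allowance.

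**Conclusion.** The point holds as an inconsistency in the stated sample-size figures, together with a modest overstatement of power. Section 3.1 cannot mean both at least 40 evaluable after 10% loss and 44 evaluable, given the cap and the absence of replacement. The dropout arithmetic falls short of 40 by 0.4 of a subject, which is minor.

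The power statement matters more. On the plan's inputs, 20 per arm gives 79.0%, 76.9% or about 75%, depending on the method, and the lowest figure belongs to the planned test. This rests on reading 20 as per arm, on equal arms and, for the Wilcoxon figure, on normally distributed data. The 39.6 assumes that the 10% refers to losses before the 4-month CBCT; the plan does not say so.

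**What to change.** In sections 3.1 and 6.3:

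- State 44 randomized (22 per center, 22 per arm), with about 40 expected evaluable, allowing four losses (9%).
- Replace evaluable with randomized wherever it is attached to 44 or to 22 per center.
- Define evaluable as having both the baseline and the 4-month CBCT, and say whether the loss allowance includes exclusions made at surgery after randomization.
- Restate power for the planned test at about 20 per arm, roughly 75 to 77%, in place of 80%, and name the method and the distributional assumption.

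The cost is a few sentences. Enrolment and the analysis do not change; the only downside is a slightly less favourable stated power.

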## 3.1.1 Visit 1: Screening

Subjects in need of ridge preservation of a single tooth extraction socket in premolars or molars prior to dental implant surgery that are deemed eligible by meeting inclusion and exclusion criteria will be considered for treatment in this study. Third molars will be excluded as a study site.

Screening process will include evaluation of general dental and systemic health. It will also include a clinical and radiographic assessment of the potential study site and the adjacent teeth. Pre-existing intraoral (periapical) radiograph can be used but must not be older than 6 months. All women except for postmenopausal women will require a negative urine human chorionic gonadotropin (HCG) test result prior to inclusion in the study to rule out pregnancy. Postmenopausal is considered when the patient has not had her period for an entire year. Eligible subjects will immediately be scheduled for Visit 2 provided that they fulfill all inclusion and none of the exclusion criterion.

#### 3.1.2 Visit 2: Enrollment

Visit 1 (Screening) and Visit 2 (Enrollment) may occur on the same day. Individuals meeting all inclusion and none of the exclusion criteria and that have signed all appropriate consent forms will be further evaluated. Before any assessment or examination is carried out for study purposes the subject must have been informed orally and in writing about the study, and have signed the appropriate consent forms. Informed consent for the research study will be given and signed on paper, as well as

VERSION 1.1 7(33)

HIPAA authorization, if not already obtained. Subjects will also be asked to sign informed consent documents.

Subjects meeting all inclusion and none of the exclusion criteria will be randomly allocated to Group A or B. Subjects with smoking habit will be stratified to be distributed equally to two treatment groups.

#### Cone beam computed tomography (CBCT) imaging

[figure not shown]
Small segmental cone beam computed tomography (CBCT) imaging will be obtained for all patients 4 months following the ridge preservation surgical procedure. Images will provide baseline data for horizontal and vertical bone locations.

A CBCT scan will be obtained using i-CAT Next Generation (Imaging Sciences International Inc., Hatfield, PA, USA) or equivalent system. Only the arch that contains the site of interest will be scanned to minimize the radiation exposure. Based on previous investigations, the field of view will be approximately 6 cm and the machine settings will be fixed at 120 kVp and 18.66 mAs for all scans.

Subject with intact ridge verified with CBCT scan is eligible to be enrolled to the study (If not, Screen failure).

VERSION 1.1 8(33)

Figure 1 Study flow chart

# 3.1.3 Visit 3: Extraction Tooth and Socket Ridge Preservation Visit 2 (Enrollment) and Visit 3 (Surgery) may occur on the same day.

Pre-Surgical, Surgical, and Post-Surgical Care (at surgical appointment)

Pre-surgical, surgical and post-surgical care will be given at the discretion of the Investigator and recorded in appropriate sections in the CRF:

- Antibiotics
- Analgesics

VERSION 1.1 9(33)

- Sedation
- Anaesthesia

#### Antibiotics:

Post-surgical antibiotic coverage will be provided to patients. The regimen is left up to the surgeon's discretion.

### Analgesics:

The regimen is left up to the surgeon's discretion.

#### Sedation:

The regimen is left up to the surgeon's discretion.

#### Anesthesia:

The regimen is left up to the surgeon's discretion.

#### **Pre-Surgical Procedures**

Buccal and occlusal photographs of the planned surgical site will be obtained. Width of keratinized mucosa on the buccal and thickness of the buccal and lingual mucosa will be measured by a caliper. Standardized periapical radiograph of a target tooth will be taken.

## Surgical Procedure

After administration of local anesthesia, the tooth will be extracted without raising a mucoperiosteal flap. A minimally invasive extraction procedure helps protection and preservation of the surrounding socket bone. Horizontal bucco-lingual ridge width at crest will be measured intraoperatively and recorded in CRF. The bucco-lingual width will be measured intraoperatively using a pointy caliper. The width will be measured 1mm apical to the alveolar crest level.

If fenestration and/or dehiscence are present when the marginal bone is sounded by a perioodontal probe through the sulcus around the tooth or fracture of the buccal bone is noted upon extraction, the subject will be excluded from the study and treated as a normal patient of the clinic (Incorrect enrollment).

After thorough debridement of granulated tissue and rinsing with sterile saline the prepared easy-graft® CLASSIC (Group A) or FDBA (Group B) will be grafted to the socket defect. Easy-graft CLASSIC should be prepared according to manufacturer's instruction. FDBA will be rehydrated by sterile saline before grafting. The graft materials will be condensed to achieve a fill of the socket to level of crestal bone.

VERSION 1.1 10(33)

A bioabsorbable collagen wound dressing (Collagen Plug, Zimmer Dental Inc.) will be placed on the top of the graft (FDBA) and secured with sutures. (Group B).

